Appendix A: Performance Status

Karnofsky Performance Scale	
Percent	Description
100	Normal, no complaints, no evidence of disease.
90	Able to carry on normal activity; minor signs or symptoms of disease.
80	Normal activity with effort; some signs or symptoms of disease.
70	Cares for self, unable to carry on normal activity or to do active work.
60	Requires occasional assistance, but is able to care for most of his/her needs.
50	Requires considerable assistance and frequent medical care.
40	Disabled, requires special care and assistance.
30	Severely disabled, hospitalization indicated. Death not imminent.
20	Very sick, hospitalization indicated. Death not imminent.
10	Moribund, fatal processes progressing rapidly.
0	Dead.

Appendix B: Study Diary

Patient Name: _____

		Please note any side effects you experienced on this day	Do not list your daily medications, but note any other medication you took on this day (both prescription and non-prescription) and the reason why taken
Monday	Date:		
Tuesday	Date:		
Wednesday	Date:		
Thursday	Date:		
Friday	Date:		
Saturday	Date:		
Sunday	Date:		

Signature of person completing form: _____

Date: _____

Appendix C: CTEP Multicenter Guidelines

If an institution wishes to collaborate with other participating institutions in performing a CTEP sponsored research protocol, then the following guidelines must be followed.

Responsibility of the Protocol Chair

- The Protocol Chair will be the single liaison with the CTEP Protocol and Information Office (PIO). The Protocol Chair is responsible for the coordination, development, submission, and approval of the protocol as well as its subsequent amendments. The protocol must not be rewritten or modified by anyone other than the Protocol Chair. There will be only one version of the protocol, and each participating institution will use that document. The Protocol Chair is responsible for assuring that all participating institutions are using the correct version of the protocol.
- The Protocol Chair is responsible for the overall conduct of the study at all participating institutions and for monitoring its progress. All reporting requirements to CTEP are the responsibility of the Protocol Chair.
- The Protocol Chair is responsible for the timely review of Adverse Events (AE) to assure safety of the patients.
- The Protocol Chair will be responsible for the review of and timely submission of data for study analysis.

Responsibilities of the Coordinating Center

- Each participating institution will have an appropriate assurance on file with the Office for Human Research Protection (OHRP), NIH. The Coordinating Center is responsible for assuring that each participating institution has an OHRP assurance and must maintain copies of IRB approvals from each participating site.
- Prior to the activation of the protocol at each participating institution, an OHRP Form 310 (documentation of IRB approval) must be submitted to the CTEP PIO.
- The Coordinating Center is responsible for central patient registration. The Coordinating Center is responsible for assuring that IRB approval has been obtained at each participating site prior to the first patient registration from that site.
- The Coordinating Center is responsible for the preparation of all submitted data for review by the Protocol Chair.
- The Coordinating Center will maintain documentation of AE reports. There are two options for AE reporting: (1) participating institutions may report directly to CTEP with a copy to the Coordinating Center, or (2) participating institutions report to the Coordinating Center who in turn report to CTEP. The Coordinating Center will submit AE reports to the Protocol Chair for timely review.
- Audits may be accomplished in one of two ways: (1) source documents and research records for selected patients are brought from participating sites to the Coordinating Center for audit, or (2) selected patient records may be audited on-site at participating sites. If the NCI chooses to have an audit at the Coordinating Center, then the Coordinating Center is responsible for having all source documents, research records, all IRB approval documents, NCI Drug Accountability Record forms, patient registration lists, response assessments

scans, x-rays, etc. available for the audit.

Inclusion of Multicenter Guidelines in the Protocol

- The protocol must include the following minimum information:
- The title page must include the name and address of each participating institution and the name, telephone number and e-mail address of the responsible investigator at each participating institution.
- The Coordinating Center must be designated on the title page.
- Central registration of patients is required. The procedures for registration must be stated in the protocol.
- Data collection forms should be of a common format. Sample forms should be submitted with the protocol. The frequency and timing of data submission forms to the Coordinating Center should be stated.
- Describe how AEs will be reported from the participating institutions, either directly to CTEP or through the Coordinating Center.
- Describe how Safety Reports and Action Letters from CTEP will be distributed to participating institutions.

Agent Ordering

Except in very unusual circumstances, each participating institution will order DCTD-supplied investigational agents directly from CTEP (See [Section 8](#)). Investigational agents may be ordered by a participating site only after the initial IRB approval for the site has been forwarded by the Coordinating Center to the CTEP PIO.

Appendix D: Preparation of PK Blood Draw Tubes and Urine Storage Cryogenic Vials With Zebularine (ZEB)

Preparation of tubes:

Zebularine (ZEB) will be provided upon request as bulk powder. Participating center pharmacies will make up a stock solution of ZEB at 100 mg/mL (wt of zebularine/volume of water added) and will prepare 1-mL frozen aliquots.

Requests for Zebularine powder can be sent to:

[name]
Pharmaceutical Resources Branch, NCI, NIH
[name]
[name]
[contact]
E-mail: [contact]

**Please note: vacutainers and/or other supplies will not be provided by the NCI*

Blood Draw Tubes:

Zebularine can be added to Vacutainer tubes up to one day in advance without causing significant loss of vacuum. Using a 3/10 cc insulin syringe or other similar sized syringe with a fine needle, draw up 30 μ L of the ZEB solution and transfer it to a 3-mL heparinized Vacutainer tube (cat # 366667) by piercing the stopper. Do not draw up ZEB for more than one tube at a time. You will not be able to control the amount of ZEB solution that leaves the needle, as it is sucked out by the vacuum. Because of the fine needle, you will not lose the vacuum (apart from the volume added) in the collection tube.

Urine Storage Cryogenic Vials:

Five (5) μ L of the 100 mg/mL ZEB solution should be added to each cryogenic vial to accommodate the 0.5 mL urine sample. Because the cryogenic tubes are not under vacuum, you can use any appropriate device to measure the 5 μ L, e.g., a micropipettor such as Pipetman. This will yield the same final concentration of ZEB in the urine samples as in the blood samples (final concentration 1 mg/mL).

Appendix E: Procedure for Blood and Urine Samples for Pharmacokinetics

Plasma:

Supplies for each sample:

- One (1) 3-mL heparinized (green-top) tube (Vacutainer® cat #366667 or equivalent) **with zebularine (ZEB, see [Appendix D](#).)**
- It is critical that the vials containing ZEB be used to minimize ex vivo deamination of FdCyd during processing and storage.
- Three (3) 1-mL cryogenic vials

Procedure: Obtain blood in a 3-mL heparinized (green-top) tube (Vacutainer cat #366667 or equivalent) preloaded with 30 μ L of 100 mg/mL of **ZEB**. Gently invert 3 times to mix and place immediately on ice. For each time point, label 3 cryogenic vials with the coordinating center patient #, date, and time. Do not include patient identifiers on the sample labels. Centrifuge the blood at 600 x g for 10 minutes at 4°C. Transfer 0.5 mL of the plasma into each of 2 cryogenic vials and the remainder of the plasma into the third cryogenic vial, if possible without disturbing the cell pellet. Keep the plasma on ice and freeze at or below -20°C within one hour.

Urine:

Supplies for each sample:

- One (1) screw-capped centrifuge tube (15 mL)
- Three (3) 1-mL cryogenic vials with 5 μ L of 100 mg/mL zebularine (ZEB, [Appendix D](#))
- It is critical that the vials containing ZEB be used to minimize ex vivo deamination of FdCyd during storage.

Procedure: Obtain approximately 10 mL of urine from the patient and place immediately on ice. Except for the pretreatment specimen, obtain the 10 mL aliquot after the total volume of the 24-hr collection has been measured. Make sure the 24-hr urine is mixed before taking the aliquot. If the aliquot is frozen, thaw on ice or thaw at room temperature, but place on ice as soon as thawed, mix, and process as soon as possible. Pour the urine specimen into a screw-capped centrifuge tube and centrifuge at 600 g for 1 minute at 4°C to sediment debris. Transfer 0.5 mL of the urine into each of 3 cryogenic vials **with ZEB**. Label the vials with the coordinating center patient # and date (no patient identifiers). Freeze the cryogenic vials of urine at or below -20°C.

All PK samples are to be shipped to:

[name], PhD
University of Pittsburgh Cancer Institute
[name]

Please notify either [name] or [name] [contact]) by telephone or [contact]) at least 24 hours prior to shipment. Samples should be shipped to arrive Tuesday,

Wednesday, Thursday, or Friday. A name, phone number, fax number, or e-mail address should be included with samples so that receipt can be acknowledged.

The shipment of human blood samples must comply with appropriate regulations as specified by the carrier. At a minimum, all samples must be packaged within two containers with absorbent material between containers to control any spill or leakage. The outer container must be puncture-resistant (e.g., cardboard mailing tube, corrugated cardboard box). A biohazard sticker must be affixed to both the inner and outer containers.

All samples should be shipped via overnight express courier in insulated containers with enough dry ice to maintain the samples in a frozen state. A copy of each of the pharmacokinetic sample collection forms for the respective patients should be included with each shipment.

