2.3 THU

Because FdCyd is phosphorylated by deoxycytidine kinase, the deamination of the nucleoside FdCyd may be inhibited without limiting its metabolism to FdUMP or its incorporation into DNA. THU is an effective non-toxic inhibitor of Cyd/dCyd deaminase, both *in vitro* and *in vivo* [55]. THU has been shown to decrease deamination of the deoxycytidine analog 1- β -D-arabinofuranosylcytosine (araC) in humans [56] and thereby to increase the potency of araC [57]. Either with or without THU, araC is only activated by deoxycytidine kinase. 1- β -D-Arabinofuranosyluridine (araU), the deamination product of araC, may have some modulatory activity but is relatively non-toxic. Decreasing the concentration of araU, *per se*, is of little benefit to the patient. Consequently, the combination of araC and THU was qualitatively the

same as araC alone. A lower dose of araC was required for activity when combined with THU, but the spectrum of activity and toxicity was the same as for araC alone [57]. In contrast to araU, FUra is not an innocuous compound and reducing patient exposure to FUra may well reduce undesired side effects of treatment with FdCyd. Improvement in therapeutic indices have been shown during *in vivo* treatment of two murine neoplasms, Lewis lung carcinoma and adenocarcinoma-755 (both the solid and ascites forms); FdCyd with THU was more effective than equitoxic doses of FUra, FdUrd, or FdCyd alone [49]. The toxicities of FdCyd have been compared with those of FUra, FdUrd, 5-fluoroorotic acid, and 5-fluorouridine in mice, rats, cats, dogs, and *Rhesus* monkeys.

Co-administration of FdCyd with THU increases the AUC of FdCyd. Using a liquid chromatography/tandem mass spectrometry (LC-MS/MS) assay developed for the quantitation of THU in plasma, co-administration of THU (100 mg/kg) with FdCyd (25 mg/kg) decreased FdCyd clearance in mice by a factor of five relative to administration of FdCyd alone (from 2.1 to 0.4 mL/min); co-administration increased the percentage of parent FdCyd recovered in 16-hour (1.61% increasing to 35.6%) and 24-hour (1.94% increasing to 21.96%) urine collections [58, 59]. FdCyd in combination with THU has demonstrated *in vitro* and *in vivo* efficacy in breast, lung, and lymphoma models [49, 54].

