9.3 Pharmacokinetics Studies (Cycle 1 Only)

FdCyd will be assayed in plasma and urine from 15 patients. Blood will be drawn from a site other than the one used to administer chemotherapy (from a contralateral limb or a central venous line of patients receiving FdCyd and THU by peripheral vein, or from a peripheral vein of patients receiving FdCyd and THU by central venous line). Urine will be collected to determine renal excretion of the drug.

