9.3.1 PK Urine and Blood Samples

Blood samples for PK analysis will be obtained from a total of 15 patients during Cycle 1 only. Samples will be collected from 3 patients from each cohort except urothelial transitional cell carcinoma; samples will be collected from 6 of the first 12 patients with urothelial transitional cell carcinoma as any ileal loops or neobladders in this patient population may have an impact on drug pharmacokinetics. One 3-mL heparinized (green-top) tube preloaded with 30 μ L of 100 mg/mL of ZEB (see [Appendix D](#) for preparation of tubes) will be obtained for each of the time points. The actual time of collection will be noted for each sample, and the sample will be placed immediately on ice. See [Appendix E](#) for reagents and the procedure for PK studies.

Blood will be collected at the following times:

- Cycle 1, Day 1 prior to treatment
- Cycle 1 Day 1 at 15 min, 30 min, 1 hr, 2 hr, and 2.5 hr during the infusion
- Cycle 1 Day 1 at 15 min, 30 min, 1 hr, 2 hr, 4 hr, and 6 hr post completion of infusion
- Cycle 1 Days 2, 3, 4, and 5 prior to treatment

Based upon the results of the initial measurements, sampling times may be adjusted but neither the total number of samples nor the total amount of blood will be increased. All samples will be immediately placed on ice. Samples should be processed within 10 minutes after collection.

A baseline urine collection of 10 mL will be collected just before drug administration. Urine will then be collected at every void from 0 to 24-hr post drug infusion on Cycle 1 Day 1 for PK analysis. Samples should be placed on wet ice immediately after collection. The total volume of urine collected for the 24-hour time period will be mixed, measured, and noted. A minimum sample of 10 mL will be saved by nursing in a specimen cup. The remainder of the unused sample can be discarded. Samples will be processed according to the procedures in [Appendix E](#).

Record the date, planned time and actual time of collection for each specimen on the pharmacokinetic form; the study number and the patient's unique patient identifier should be included on this form. In addition, the date and exact time when the FdCyd and THU doses were administered should be recorded on the appropriate pharmacokinetic form ([Appendix G](#)).

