Send each sample when drawn to local lab for processing and interim storage according to [Appendix E](#) for Pharmacokinetic (green-top) samples and [Appendix F](#) for Pharmacodynamic (lavender-top) and CTC (CellSave) samples.

Urine Collection Guidelines for the First 24 Hours Post-Drug Administration

Collect and pool urine for the first 24 hours post drug (0-24 hours), and refrigerate. Please note the total volume of urine collected. At end of 24 hours, mix the urine and take a 10 mL aliquot in a sterile urine cup, refrigerate, and discard the rest.

Sample Collection for Day 1 continues on the next page.

Combined Specimen Collection Form (**PK/PD Flow Sheet**) for Pharmacokinetic and Pharmacodynamic Studies for Cycle 1 – Page 2 of 4

Cycle 1, Day 1:

Patient ID

Date	Hr:Min	Sample	Planned Time	Actual Time	RN	Comments
Important – Record time						
(Day 1, Cont.)			infusion started	:		
	:	#5 (P2)	15 Minutes - 3 mL of blood in a green-topped tube with ZEB	:		
	:	#6 (P3)	30 Minutes - 3 mL of blood in a green-topped tube with ZEB	:		
	:	#7 (P4)	1 Hour - 3 mL of blood in a green-topped tube with ZEB	:		
	:	#8 (P5)	2 Hours - 3 mL of blood in a green-topped tube with ZEB	:		
	:	#9 (P6)	2.5 Hours - 3 mL of blood in a green-topped tube with ZEB	:		
Important – Record time						
(Day 1, Cont.)			infusion ended	:		
	:	#10 (P7)	15 Minutes - 3 mL of blood in a green-topped tube with ZEB	:		
	:	#11 (P8)	30 Minutes - 3 mL of blood in a green-topped tube with ZEB	:		
	:	#12 (P9)	1 Hour - 3 mL of blood in a green-topped tube with ZEB	:		
	:	#13 (P10)	2 Hours - 3 mL of blood in a green-topped tube with ZEB	:		
	:	#14 (P11)	4 Hours - 3 mL of blood in a green-topped tube with ZEB	:		
	:	#15 (P12)	6 Hours - 3 mL of blood in a green-topped tube with ZEB	:		

Send each sample when drawn to local lab for processing and interim storage according to [Appendix E](#).
Sample Collection for Days 2-5 begins on the next page.

Combined Specimen Collection Form (**PK/PD Flow Sheet**) for Pharmacokinetic and Pharmacodynamic Studies for Cycle 1 – Page 3 of 4

Cycle 1, Days 2-5:

					Patient ID	
Date	Hr:Min	Sample	Planned Time	Actual Time	RN	Comments
Ask patient to void just before ending urine collection.						
(Day 2)	:	#16 (U2)	Before Day 2 Chemo - End of 24-Hr urine collection	:	_____	
	:	#17 (P13)	Before Day 2 Chemo - 3 mL of blood in a green-topped tube with ZEB	:	_____	
(Day 2, Cont.)	Important – Record time infusion started					:

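### Appendix E lets the 10 mL PK urine aliquot be frozen and thawed before any ZEB is added, although it calls ZEB critical during urine storage

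*Combined protocol and SAP*

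**What the plan says.** Section 9.3 gives one purpose for the urine: "Urine will be collected to determine renal excretion of the drug". Section 9.3.1 sets the collection window, "Urine will then be collected at every void from 0 to 24-hr post drug infusion on Cycle 1 Day 1 for PK analysis", and the holding condition, "Samples should be placed on wet ice immediately after collection". Appendix G words the holding differently: "Collect and pool urine for the first 24 hours post drug (0-24 hours), and refrigerate". After 24 hours the pool is mixed and measured, about 10 mL goes into a cup that is refrigerated, and the rest is discarded.

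Appendix E then takes over. On the aliquot it says: "If the aliquot is frozen, thaw on ice or thaw at room temperature, but place on ice as soon as thawed". The urine is next centrifuged, and 0.5 mL goes into each of three cryovials that hold ZEB. On those vials it says: "It is critical that the vials containing ZEB be used to minimize ex vivo deamination of FdCyd during storage". The matching statement for plasma is wider: "It is critical that the vials containing ZEB be used to minimize ex vivo deamination of FdCyd during processing and storage". For plasma, ZEB is in the tube before the blood is drawn.

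**The concern.** Section 2.2 describes deamination as the necessary first step in FdCyd breakdown, and ZEB is there to stop it outside the body. The cryovials carry ZEB even though they are frozen at or below -20°C, so the plan does not treat cold alone as enough for stored urine. Yet the 10 mL aliquot, which is the source of all three cryovials, may itself be refrigerated or frozen without ZEB for an unstated time.

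Parent drug lost at that stage would be read as drug not excreted, so the error runs in one direction. It would also be hard to recognise later: Section 9.3 names FdCyd and no deamination product for the urine assay, and the rest of the pool has been discarded.

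**Working it through.** **Order of steps for urine, from Section 9.3.1 and Appendices D, E and G**

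| Step | Condition | ZEB present? |
|---|---|---|
| Voids, 0–24 h | wet ice (9.3.1) or pooled and refrigerated (App. G) | none stated |
| 10 mL aliquot in cup | refrigerated, no time limit (App. G) | none stated |
| Aliquot, if frozen | frozen, then thawed on ice or at room temperature (App. E) | none stated |
| Centrifugation | 4°C (App. E) | none stated |
| Three 0.5 mL cryovials | at or below -20°C (App. E) | yes |

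No section adds ZEB to the container, the pool or the cup.

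**The plan's own figure.** Appendix D states a final ZEB concentration of 1 mg/mL.
- Urine vial: 5 µL × 100 mg/mL = 0.5 mg in 0.5 mL = 1.00 mg/mL (0.5/0.505 = 0.990 counting the added volume).
- Blood tube: 30 µL × 100 mg/mL = 3 mg in 3 mL = 1.00 mg/mL (3/3.03 = 0.990).

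The figure reproduces and is not in dispute.

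**Number of patients.** 3 × 3 + 6 = 15.

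**Possible size.** The documents report no rate of FdCyd loss in urine without ZEB. The rates below are assumptions, with a constant hourly fraction r lost over h hours: loss = 1 − (1 − r)^h.

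| Assumed r per hour | 12 h | 24 h |
|---|---|---|
| 0% | 0% | 0% |
| 0.1% | 1.2% | 2.4% |
| 0.5% | 5.8% | 11.3% |
| 1% | 11.4% | 21.4% |
| 2% | 21.5% | 38.4% |

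The 24-hour column is an illustration, not an upper bound, because the time the aliquot may wait is not limited. Equally, nothing in the documents excludes the first row.

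**ZEB needed to protect the aliquot.** 10 mL × 1 mg/mL = 10 mg, which is 10/100 = 0.1 mL of stock (10/10.1 = 0.990 mg/mL counting the added volume). For 15 patients with one post-dose aliquot each, 15 × 10 = 150 mg.

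**The case against.** The best defence is that the authors drew a distinction. The plasma statement covers processing and storage, while the urine statement covers storage only. Chilled collection may therefore have been judged acceptable, and THU excreted by the patient might also slow deamination. Freezing the aliquot is only a contingency, and prompt handling after thawing is required. PK is not among the objectives in Sections 1.1 and 1.2, and Section 13 contains no PK analysis.

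Much of this stands. A reader might infer that the whole 24-hour chilled collection contradicts Appendix E; given the narrower urine wording, the text does not clearly show that. The defence does not cover the aliquot, because a frozen cup of urine is in storage by any ordinary meaning. The documents report neither urinary THU nor the stability of urine without ZEB.

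Two further inferences are tempting and should not be made.
- **Mouse recoveries.** Section 2.3 reports: "co-administration increased the percentage of parent FdCyd recovered in 16-hour (1.61% increasing to 35.6%) and 24-hour (1.94% increasing to 21.96%) urine collections". With THU, the 24-hour figure is 38% below the 16-hour figure (1 − 21.96/35.6 = 0.383), which might look like loss in the container. Without THU, recovery rises by about 20% (1.94/1.61 = 1.205), whereas container loss should be at least as great with no inhibitor present. The text does not say that the two collections shared animals, regimen or handling.
- **Urinary diversion.** Six urothelial patients are sampled because ileal loops or neobladders may alter PK, so a reader might fear that handling loss would mimic a diversion effect. All 15 patients follow the same written procedure. A loss common to all does not create a difference between groups, and nothing in the documents suggests faster loss in diverted urine.

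**Conclusion.** The point holds for the 10 mL aliquot. Appendix E calls ZEB critical during urine storage and also permits that aliquot to be frozen and thawed without it; Appendix G refrigerates it without ZEB and without a time limit. If FdCyd is lost in that interval, urinary FdCyd and renal excretion are understated in up to 15 patients.

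The size cannot be computed from the documents. The range of 0 to 38% over 24 hours rests entirely on assumed constant rates of 0 to 2% per hour. The documents do not show that a loss occurs. Plasma PK, where ZEB is in the draw tube, is untouched, as are response rate and PFS. Severity is minor; the change is worth making because it costs almost nothing.

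**What to change.** 1. In Appendix E, delete the sentence that provides for a frozen aliquot, and state that no PK urine is frozen before it is in ZEB.
2. Choose one of two ways to protect the aliquot:
   - Put ZEB in the aliquot cup: 0.1 mL of the 100 mg/mL stock per 10 mL, scaled to the volume actually saved because Section 9.3.1 sets 10 mL as a minimum. Appendix D then needs a line for the cup. It should also say whether the cryovials are still preloaded, since doing both gives about 2 mg/mL.
   - Transfer urine to the ZEB cryovials as soon as the 24-hour collection has been mixed and measured.
3. Give one chilled holding condition for the 24-hour collection in Section 9.3.1 and Appendices E and G, in place of the present mix of wet ice, refrigeration and possible freezing.

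Sampling a fixed fraction of every void into a preloaded tube is not recommended. The final volume is unknown in advance, so the ZEB concentration could not be set, and repeated small transfers would add volume error.

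The cost is a small wording change and, with ZEB in the cup, about 10 mg of ZEB per 10 mL aliquot. The number of assay samples does not change.
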